Protocol

“A Quick pathway for patients with high pRobability of dislocatEd hemi- or total hip arthroplasty to minimize the time from hospital aDmission to redUCtion of the prosthEsis”

the Q-REDUCE study

- a prospective cohort trial

Main investigator:

[name] [name], PhD, post.doc.
Dept. of Orthopedics, Esbjerg Hospital
University Hospital of Southern Denmark
Dept. of Regional Health Research
University of Southern Denmark, Odense

Co investigators:

[name] & [name] [name]
Dept. of Anesthesiology, Esbjerg Hospital
University Hospital of Southern Denmark

[name] [name], PhD, Head of Research
Dept. of Radiology, Esbjerg Hospital
University Hospital of Southern Denmark

[name], Head of Research
Dept. of Emergency Medicine, Esbjerg Hospital
University Hospital of Southern Denmark

Background:

Most patients undergo elective total hip arthroplasty (THA) due to primary osteoarthritis (OA) (80%). The remaining 20% are indicated by secondary arthritis as a consequence to earlier fracture surgery, hip dysplasia, rheumatism or tumors (1). Additionally, hip replacements are also performed in acute cases such as displaced femoral neck fractures, in which hemiarthroplasties (HA) often are preferred as opposed to THAs, depending on the surgeon's preference and skills. The patient categories differ significantly, with the acute fracture patients being older and more comorbid, thereby more fragile (2). Annually, 10,500 THAs and 2,100 HAs are implanted nationally, while the count is 2,100 THAs and 550 HAs in the Region of Southern Denmark (1, 3).

Despite being a highly successful procedure in terms of both safety and patient satisfaction, complications after hip replacements do still occur (4). One of the most common complications and reason for hip revisions is hip dislocation. After THA, it occurs in 3,5% of primary OA patients within the first two postoperative years, while the incidence is higher in other patient categories, e.g. fractures (2, 5, 6). The risk of dislocation after HA is reported between 6% - 11% (7, 8).

The dislocated prosthesis is usually managed by a simple, closed reduction maneuver under general anesthesia with or without muscle relaxation, resulting in open surgical reduction rarely being needed (9-11). Time from admission to actual reduction often includes various steps (incl. several patient transfers between emergency units, radiology departments, operating theaters) which causes an unnecessarily long period of pain for the patient. In 2015, a fast-track system was introduced at Hvidovre Hospital on a trial basis for patients highly suspected for THA/HA dislocation (12). This resulted in a significant decrease in the time from arrival to reduction and overall time of hospitalization, without resulting in more complications. The study was retrospective and did not measure how patients experienced the change in practice.

A fast-track system must be specially designed for the local departments, due to differences in the logistical options from hospital to hospital. The purpose of this study is to design a fast-track pathway for patients referred to the University Hospital of Southern Denmark, Esbjerg, with high probability of having a dislocated hip prosthesis with the primary aim to reduce the time from arrival to reduction and the total hospitalization time. Secondary aims are to

- investigate whether quicker prosthesis reduction influences on hip function and quality of life afterwards
- reduce the pain experience immediately and in the long term
- increase patient satisfaction

without changing the overall complication rate and readmission/mortality

Methods:

Trial design

The study is designed as a prospective observational cohort trial, adhering to the STROBE guidelines (13). The present protocol will be registered at clinicaltrials.org and submitted for publication in an international journal.

Setting

The study is conducted at the University Hospital of Southern Denmark, Esbjerg, as a collaboration between the Department of Orthopedics, Department of Anesthesiology, Department of Radiology, and Department of Emergency.

The study is planned to start September 1st, 2024, and will continue for two years. During the first year, the admitted patients will follow the current standard treatment pathway. After September 1st, 2025, a newly developed treatment pathway will be adhered to, and for the rest of the protocol, this pathway is described as the Fast-track pathway, as the expectation is that treatment strategy will shorten time to reduction.

All patients admitted with a dislocated THA or HA will be included in the study without prior informed consent. The patients are – disregard of cognitive status – admitted with a complication that requires acute treatment. After the acute treatment (reduction of the dislocated prosthesis), the patients are informed about the study and encouraged to participate in the second part of the study (see outcome section).

Participants

Inclusion criteria: All adult patients admitted to the Department of Emergency Medicine (Dept. of EM), University Hospital of Southern Denmark, Esbjerg, for suspected dislocated hip prosthesis who fulfills the following

- age > 18 years
- a history of either a THA or a HA in combination with at least one of the following terms:
 - having sustained a sudden, incorrect movement or twist in the hip joint in either a bending, sitting or supine position leading to inability to stand or walk
 - misalignment of the concerned lower extremity (typically shortened, with inward/outward rotation)

Exclusion criteria: Patients with

- recurrent dislocations during the same hospital admission (already “in the house”)
- anticipated difficult airway by the attending anesthesiologist
- anticipated need for extended respiratory or hemodynamic monitoring by the attending anesthesiologist
- American Society of Anesthesiologists (ASA) score > 3
- Body Mass Index (BMI) > 40
- active drug abuse
- contraindication for Propofol or Esketamine

Intervention

Referred patients will follow either the standard pathway or a newly developed fast-track pathway, specifically designed with regard of the local logistics and structure at the Dept. of EM, University Hospital of Southern Denmark, Esbjerg.

Patient reported to the coordinating nurse at the Department of Emergency Medicine, fulfilling the inclusion criteria's, without violating exclusion criteria's	
Standard Pathway (September 2024 - August 2025)	Fast-track Pathway (September 2025 - August 2026)
Patient arrival through the ambulance entrance	Patient arrival through the ambulance entrance
Patient admitted to the Dept. of EM ward (Team 1 or 2), and transferred to a regular, standard patient bed	Patient is delivered directly to emergency trauma room no. 4 (located in conjunction of the ambulance entrance), and transferred to a radiolucent trauma bed
Patient is seen by the delegated nurse; vital parameters measured and registered, together with patient information	The orthopedic doctor AND the anesthesiologist on duty is notified and will arrive to the trauma room at their earliest convenience, depending on other acute activities
Patient is examined by one of three doctors on duty from the Dept. of Orthopedics, when	Patient is seen by the delegated nurse; vital parameters measured and registered, together with patient information, and X-ray is ordered

available (varying degree of education), and X-ray is ordered	
Patient is moved to the X-ray room (same floor level), (transfer to a special X-ray bearing is required) and will be returned to the bed ward	The diagnosis is verified by X-ray on site, by transportable X-ray machine, carried out by the radiology staff, without the need for patient transfer
Diagnosis is verified and the patient's medical files is updated	Patient's medical files is updated by the orthopedic doctor on duty (a standard paragraph will be developed for quick documentation in the medical records)
Patient is booked for a closed reduction maneuver in the operating theater during a short general anesthesia	The anesthesiologist on duty prepares for local sedation, following the sedation algorithm designed for this study, assisted by an anesthesiology nurse
Patient is reported to the anesthesiologists on duty for the purpose of planning and preparation for the anesthetic procedure	Closed reduction is completed, and control X-ray is conducted immediately on site, by transportable X-ray machine, carried out by the radiology staff, without the need for patient transfer
Patient is transferred to the operating theater, depending on other surgical activities and fasting time	Patient is transferred to the Dept. of EM ward
Closed reduction is completed during a short general anesthesia, often with simultaneous muscle relaxation. Patient is transferred back and forth to a surgical bearing to confirm reduction, using a C-arm X-ray (not useful for documentation)	Patient is seen by a physiotherapist and mobilized with/without walking aids
Patient return to the Dept. of EM bed ward	Patient is discharged with/without a planned outpatient follow-up by a hip surgeon, depending on the specific patient case
Patient is moved to the X-ray room for a control X-ray (same floor level), (transfer to a special X-ray bearing is required) and will be returned to the bed ward	
Patient is seen by a physiotherapist and mobilized with/without walking aids	

Patient is discharged with/without a planned outpatient follow-up by a hip surgeon, depending on the specific patient case	
--	--

Assumed fast-track advantages includes

- elimination of several patient transfers back and forth from the Dept. of EM bed ward to X-ray rooms and operating theater (saves **time** and **hospital resources**)
- elimination of several patient transfers between different beds (reduces **patient pain** and **discomfort**)
- hip reduction in sedation rather than general anesthesia disregard of fasting time, - safely administered by anesthesiologists rather than by the orthopedic (saves **time**, increases **safety**)

Detailed description of standard anesthetic procedure for patients enrolled for standard pathway hip reduction (current practice)

Patients following the standard pathway and local guidelines, will receive a general anesthesia with a rapid sequence induction and intubation using Propofol 1-2 mg/kg, Alfentanil 0,2-0,3 mg/kg or Fentanyl 2-3 µg/kg and Suxamethonium 1 mg/kg. The patient is as a standard monitored with non-invasive blood pressure, saturation, pulse, 3-point ECG and end-tidal CO₂. More extensive monitoring may be used if considered necessary by the attending anesthesiologist.

Detailed description of new fast-track sedation procedure for patients enrolled for fast-track hip reduction

The goal for the new fast-track sedation pathway is a short deep sedation, according to the definition of level of sedation by ASA (14). This is for optimal patient comfort and success and with very low risk of aspiration (15, 16). The patient is sedated with Propofol 0,5-1 mg/kg and/or Esketamine 0,1-0,5 mg/kg. If a repeat dose is necessary, it is with Propofol 0,2 mg/kg and/or Esketamine 0,1-0,5 mg/kg (17, 18). Before sedation an intravenous line is placed with 1 L Ringer Acetate and the patient will receive a nasal cannula with an oxygen flow of 2-5 L/min. During the sedation the patient is monitored with a non-invasive blood pressure, saturation, respiratory rate, pulse and 3-point ECG and the nurse anesthetist and anesthesiologist will continuously observe the depth of sedation and respiratory drive. After the hip reduction, the patient is observed and monitored until the sedation has worn off and there is no risk of airway obstruction.

Outcomes

The *primary* outcome is time from arrival at the emergency entrance to prosthesis reduction.

The *secondary* outcomes are:

- a) total hospitalization time from arrival to discharge
- b) intra-operative complications (fracture, unsuccessful reduction, aspiration, need for mask ventilation and/or intubation, others)
- c) post-operative complications (cardiac, pulmonal, thrombo-embolic events, nerve damage, re-dislocation, others) during hospitalization
- d) 30 days re-admission
- e) 30- and 90-days mortality
- f) hip-related pain measured by a 10-digit numeric rating scale (NRS)
- g) patient-reported outcome (PRO) using the Hip disability and Osteoarthritis Outcome Score (HOOS), domains ¹⁾PAIN, ²⁾OTHER SYMPTOMS, ³⁾FUNCTION IN DAILY LIVING, AND ⁴⁾HIP-RELATED QUALITY OF LIFE (19)
- h) Health-related quality of life using the EQ-5D questionnaire (20)
- i) patient satisfaction
- j) time consumption by the involved staff (orthopedic, anesthetic, radiology staff etc.)
- k) total hospital costs during admission

Every admitted patient will be included for evaluation of the primary and secondary outcomes (a-e + j-k) regardless of the patient's cognitive status. However, the remaining secondary outcomes (f-i) will require that the patient is able to understand the Danish language and cognitively able to answer the questions meaningfully. A dedicated project nurse will assist during the hospital admission if required. A patient can be included several times due to recurrent dislocations which will be accounted for during statistical analysis.

Outcome/variable time table

Pre-admission (recall past 14 days)	Hospital ad- mission (Day 0)	Day 1	Day 3	Day 7	Day 14	Day 30	Day 90	Day 180	Day 365
Patient-reported outcomes									
NRS	NRS	NRS	NRS	NRS	NRS	NRS			
HOOS					HOOS		HOOS	HOOS	HOOS
EQ-5D					EQ-5D		EQ-5D	EQ-5D	EQ-5D
	Satisfaction								
Registry/Patient file outcomes									
	Time to reduction								
	Time to discharge								
	Per-operative Complications								
	Post-operative complications								
						Re- admissions			
						Mortality	Mortality		
Patient variables									
	Age								
	Sex								
	ASA-score								
	BMI								
	Specific comorbidities								
Prosthesis variables									
	Primary operation date								
	No. of previous dislocations								
	Type of prosthesis (incl. liner type)								

Information acquired from patient files: Information regarding patient-related factors (age, sex, ASA-score, BMI, and specific comorbidities) and prosthesis-related factors (primary operation date, number of previous dislocations, and type of prosthesis), as well as information regarding

30-days readmission and mortality, and 90-days mortality will be acquired from the patient files after acquired patient consent. The patient- and prosthesis-related factors will be used to control for potential confounding. The acquired patient file information is dated from admission to 90 days post-admission. The prosthesis-related information is dated to the primary operation date. We will only access patient files from patients who accept to participate, therefore 120 patients.

As the acute treatment has been performed when the patient is asked for consent, we apply for the use of the data acquired during the acute treatment of the patient, regardless of whether they choose to participate in the secondary part of the study regarding the patient-reported outcomes, in order to not prolong the study unnecessary. This includes the patient- and prosthesis-related factors, as this will be used to control for potential residual confounding.

Sample size

Study sample size are based on the primary outcome “Time from arrival at the emergency entrance to prosthesis reduction”, applying a formula for RCT studies with clinically superiority design (21). The null-hypothesis dictates no difference in time from arrival at the emergency entrance to prosthesis reduction for patients following the Standard Pathway or the Fast-Track Pathway.

$$N = 2 \times \left(\frac{z_{1-\alpha} + z_{1-\beta}}{\delta - \delta_0} \right)^2 \times s^2$$

N = no. of patients in each group

Alpha-value = 0,05 (5% risk of type-1 error)

Beta-value = 0,90 (10% risk of type-2 error)

Delta-value (estimated true value between the two groups) \approx 4 hours

Delta₀-value (estimated clinical acceptable difference between the two groups) \approx 3 hours

S-value (pooled standard deviation (SD) for both groups) \approx 2.5 hours

A review of 16 randomly selected patients that was admitted to the University of Southern Denmark, Esbjerg, with a dislocated THA from January 2018 to May 2022 revealed a mean time from arrival at the emergency entrance to prosthesis reduction at 6 hours (range 2.7 – 9.0 hours) with a standard deviation at 1.6 hours.

$$N = 2 \times \left(\frac{1,645 \times 1,28}{4 - 3} \right)^2 \times 2,5^2 \approx 53 \text{ patients in each group}$$

Based on a review of the surgical procedures performed during the period 01.02 – 31.08.2022, we expect to admit 5-6 patients per month with a dislocated THA or HA, and we expect an attendance rate of >90% based on the primary outcome. Therefore, we will include 53 patients + 15% ≈ 60 patients in each group, due to the risk that specific comorbidities will lead to exclusion from the Fast-Track pathway by the anesthetic staff. It is thus expected that a total of 120 patients will be adhered to one of the two treatment algorithms over the course of 24 months.

Blinding

This study concerns emergency research without the possibility of informed consent prior to intervention, and the patients will not be informed regarding their participation in a scientific study on arrival. Post-reduction, the patients are encouraged to participate in the second part of the study involving patient-reported outcome measures. The patient will not be informed of whether they have been adhered to the standard or Fast-track treatment strategy and are therefore blinded regard the treatment.

The orthopedic and anesthetic staff are not informed regarding the initiation of the current study and are therefore blinded in terms of the aim. The staff will be thoroughly instructed to adhere to the Fast-track strategy at the time for pathway shift.

Patient information

After reduction of the prosthesis, the patients are admitted to the ward at the Dept. of EM, regardless of the treatment received. During the admission, the patient will be interviewed by a dedicated study-nurse and informed about the study, without revealing the allocated treatment pathway. The rooms are single-patient only, in order to secure that the information can be given undisturbed. The patients will be screened for eligibility (cognitive status, language) for participation in the secondary part of the study, and the nurse will deliver patient information including a study overview depicting the timepoints for evaluation. When recruiting the patient for the secondary part of the project, it is stated that this is a scientific trial and that the patient has the right to have a companion present during the information. The patients are encouraged to respond before discharge, typically 12-24 hours after arrival.

Up to 15-20% of patients admitted to the hospital with a dislocated THA/HA is cognitively impaired due to dementia in a degree that hinders reasonable questionnaire response. These patients require the same acute treatment as any other patient, and there is no reason for not including them in this study. Information will be given to the patient's relatives, and we will ask for their permission to include the already obtained journal data in the study.

Patent information folder is found in the appendix (in Danish).

The patients are informed that consent gives the trial manager, sponsor and sponsor's representatives as well as any supervisory authority direct access to obtain information in the patient's medical record, etc., including electronic medical records, in order to see information about the subject's health, which is necessary as part of the implementation of the research project and for control purposes, including self-control, quality control and monitoring, which they are obliged to carry out.

Statistics

Mean values with standard deviation (SD) are given for normally distributed data, while median values with interquartile range (IQR) are given for skewed data. In case of normally distributed data, two-sample t-test is used. Mann-Whitney U-test is used to compare continuous nonparametric variables and chi-square test is used to compare categorical variables. STATA version 18 will be used for all statistical analyses.

Economy

The main investigator and initiator is [name], Ph.D., post.doc.

The study is conducted as a collaboration between the Department of Orthopedics, Department of Anesthesiology, Department of Radiology, and Department of Emergency Medicine, University Hospital of Southern Denmark, Esbjerg. There are no special economics involved in the study between the departments, as the study is carried out as a part of normal daily, acute activity.

Vestjysk Orthopedic Fund will be applied for covering expenses to hardware (computer, Ipad etc.)

The Region of Southern Denmark's Research Fund will be applied for covering salary to a dedicated study nurse.

Grants are administered via an account that is subject to public audit.

There are no conflicts of interest.

Ethics

Permission to store and handle data is obtained upon application to the Region of Southern Denmark's internal register (24/34681). The Danish Law of data protection is observed.

The regional ethics committee has been applied for permission to conduct the study under special circumstances as acute research without the possibility of obtaining informed consent from the

patient prior to intervention. The purpose and hypothesis of this study can simply not be investigated if the patients are admitted as usual and permitted time for consideration to participate or not. This group of patients suffers from a complication (a dislocated hip arthroplasty) that requires intervention (reduction of the prosthesis) as quick as possible, regardless of the patient's cognitive status. There is only one treatment to this specific complication, and thus they will all receive the same surgical intervention whether they participate in the study or not. There is no reason to believe that the patients are exposed to greater risk by the Fast-Track pathway than Standard pathway. On the contrary, it is strongly expected that the patients will be treated significantly quicker during a smooth concept, thereby reducing the period in pain. Reduction in the emergency department (Fast-track pathway) is more likely to be even safer than current practice (due to the participation of the anesthesiologists), where the emergency staff and orthopedics are responsible for sedation outside the operating theater. The regional ethics committee has responded that the study does not require their permission, and the study can be conducted as a treatment-quality study, locally approved by the Executive Board at the University Hospital of Southern Denmark.

X-ray radiation dose:

The patients will be exposed for two different X-ray systems, depending on randomization. The patients following the standard pathway is transferred to a room, where a fixed, stationary X-ray system is applied, whereas a smaller, transportable X-ray machine is used for the patients randomized to the fast-track pathway. We have made a pre-liminary measurement of the radiation dosage to compare the two interventions. The conventional, standard machine exposes the patient for 0.1258 milliSievert (mSv), whereas the number is 0.1102 mSv for the mobile device. Therefore, our new pathway do not expose the patients for higher radiation doses. The annual background radiation in Denmark is 3-5 mSv, so the radiation doses are negligible and the study is categorized as IIa and justifiable if it leads to increased knowledge and health advantages. The lifetime cancer risk in Denmark is approx. 25%. This risk increases 5% pr. Sievert. Thus, participation in the study will increase the cancer risk to 25.0001%.

Patient insurance:

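### Outcome c counts post-operative complications only until discharge, so its observation window after reduction can differ between pathways, in either direction

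*Protocol*

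**What the plan says.** The Outcomes section of the Protocol lists secondary outcome c as "post-operative complications (cardiac, pulmonal, thrombo-embolic events, nerve damage, re-dislocation, others) during hospitalization". The Outcome/variable time table places it under the hospital admission column only. Re-admission (d) has a fixed window of 30 days, and mortality (e) has windows of 30 and 90 days.

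The Background describes the fast-track pathway "with the primary aim to reduce the time from arrival to reduction and the total hospitalization time", and adds that this should happen "without changing the overall complication rate and readmission/mortality". Total hospitalization time is itself secondary outcome a.

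Re-dislocation appears in three places. It is an item of c. Under Participants, "recurrent dislocations during the same hospital admission" are excluded from new inclusion. Under Outcomes, "A patient can be included several times due to recurrent dislocations".

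On data sources, the section on information from patient files states: "The acquired patient file information is dated from admission to 90 days post-admission". It ties the 30-day data to patient consent. For other patients, the paragraph that follows seeks only data from the acute treatment.

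**The concern.** A complication count that ends at discharge compares the pathways fairly only if patients are observed for similar lengths of time after reduction. Here the end of observation is something the intervention is meant to change. Two pathways with the same true risk could then show different values of c, and one event could fall under c or under d purely because of when the patient went home.

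Outcome c carries part of the safety condition attached to the aim. Outcomes d and e pick up later events only if they lead to re-admission or death. Nerve damage, or a thrombo-embolic or cardiac event managed without re-admission, is not recorded once the patient has left.

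Outcome b has a smaller, related problem. It lists the need for mask ventilation and/or intubation with no qualifier, although the description of the standard anesthetic procedure includes intubation as the planned technique.

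**Working it through.** **Can the post-reduction stay differ?** The pathway table under Intervention gives these steps after reduction:

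- Standard: return to the emergency ward, then "Patient is moved to the X-ray room for a control X-ray (same floor level"), return to the ward, physiotherapy, discharge.
- Fast-track: "Closed reduction is completed, and control X-ray is conducted immediately on site", then ward, physiotherapy, discharge.

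The standard column therefore has an extra transfer after reduction. No duration is given for it, and most of the differences between the columns come before reduction. A difference in post-reduction stay is possible, but its size and direction cannot be read from the Protocol.

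**Where does a re-dislocation go?** Before discharge it counts in c and cannot open a new inclusion. After discharge it no longer counts in c and appears as a re-admission (d) or a new inclusion. It is not lost, but discharge time alone decides its category.

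**Illustration of size.** The Protocol states no figure for c, so there is none to reproduce.

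Inputs from the Protocol:
- Mean time from arrival to reduction in current practice: 6 h (Sample size).
- Expected difference between pathways: about 4 h (Sample size), so fast-track reduction at 6 − 4 = 2 h.
- Discharge typically 12–24 h after arrival, not split by pathway (Patient information).
- 60 patients per group (Sample size).

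Assumptions: standard stay 24 h; fast-track stay 12, 18, 20 or 24 h; in-hospital risk p of 2%, 5% or 10% under standard; constant hazard, equal in both pathways.

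Standard window after reduction: 24 − 6 = 18 h.

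Window ratio = (fast-track stay − 2)/18. Risk shown under fast-track = 1 − (1 − p)^ratio.

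| Fast-track stay | Ratio | p = 2% | p = 5% (events in 60) | p = 10% |
|---|---|---|---|---|
| 12 h | 10/18 = 0.556 | 1.1% | 2.8% (1.7) | 5.7% |
| 18 h | 16/18 = 0.889 | 1.8% | 4.5% (2.7) | 8.9% |
| 20 h | 18/18 = 1.000 | 2.0% | 5.0% (3.0) | 10.0% |
| 24 h | 22/18 = 1.222 | 2.4% | 6.1% (3.6) | 12.1% |

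The 20 h row is the case in which only the 4 h before reduction are saved, and it shows no bias. The 24 h row, with total stay unchanged, gives fast-track the longer observation. The 12 h row pairs the two ends of the stated discharge range and is an extreme.

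**Would it be mistaken for a real effect?** With 60 per group and a two-sided 5% test of two proportions, the chance of significance in the direction of the artefact is Φ((|d| − 1.96·SE₀)/SE₁). Here d is the difference in risk, SE₀ the pooled and SE₁ the unpooled standard error. For the 12 h row this gives 0.09 at p = 5% and 0.14 at p = 10%. For the 24 h row it gives 0.04 and 0.06. A false significant result is unlikely, so the problem is how the observed rates are read.

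**How much follow-up does c have?** At most 22 h after reduction in these cases: 22/720 = 3.1% of a 30-day window.

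**The case against.** The strongest reply is that the bias is hypothetical. The pathways differ mainly before reduction, afterwards both go through ward, physiotherapy and discharge, and the Protocol gives no reduction-to-discharge time by pathway. This stands, and it is why the point is conditional.

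A reader might infer that c will make fast-track look safer. The documents do not support that. The bias can run either way or be absent, depending on where time is saved.

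The constant hazard is also open to doubt. If procedure-related events cluster soon after reduction, a change in discharge time matters less than the table shows. The 12–24 h range comes from a sentence about when patients are asked to respond, and is not a measured stay. Both points stand, so the table is an illustration and not an estimate.

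Later events are partly covered. Outcomes d and e have fixed windows, and a re-dislocation after discharge is still recorded elsewhere. Excluding same-admission recurrences from new inclusion while counting them in c also avoids double counting. The remaining gap is misclassification between c and d, and the loss of post-discharge events managed without re-admission.

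An in-hospital count also has merits. It does not need the consent-dependent 30-day data, and it takes in fewer background events unrelated to the reduction. That is a reason to keep it, but it does not make the window comparable.

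On outcome b, a literal reader might infer that nearly every standard-pathway patient would count as having a complication. The item speaks of need and stands among intra-operative complications, so planned intubation is not its natural meaning. A short qualifier is enough.

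**Conclusion.** The point holds as a minor design weakness. Outcome c ends at discharge, the intervention aims to bring discharge forward, and the observation time after reduction can therefore differ between pathways in either direction. Events after discharge that do not lead to re-admission are not counted, which limits what c can say about an unchanged complication rate.

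Under the assumed stays, a constant hazard and a 5% risk, equal true risk would show as 2.8% to 6.1% under fast-track against 5.0% under standard, about 1.7 to 3.6 events against 3.0 in 60. The less extreme cases differ from standard by about 0.3 to 0.6 events. If only time before reduction is saved, there is no difference. The primary outcome and the sample size are not affected.

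**What to change.** Add a count of the outcome c items over one fixed window from reduction, the same in both pathways, for example 30 days. Take it from the file review already planned for 30-day re-admission. Use this count for the comparison between pathways, and report the in-hospital count for all patients alongside it. State that a re-dislocation within the window counts for the index episode, whether or not it also opens a new inclusion. Under equal hazard and complete follow-up, the expected ratio between pathways is then 1.00 whatever the time of discharge.

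In outcome b, qualify the airway item as unplanned, meaning beyond the planned technique of the pathway.

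The cost is a change of wording and a little more extraction, since file data are already dated to day 90. Coverage would be the same consent-limited coverage as for d: at an assumed 80% to 90% file access, 0.80 × 60 = 48 to 0.90 × 60 = 54 patients per group. Events treated elsewhere may be missed.
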